5.5.2.10. Histologic assessments

Histologic endpoints - GHAS

- Change from baseline in the Ileal GHAS score at Week 12, Week 48, and Week 96 (among participants with Ileal histologic disease at baseline per GHAS)
- Change from baseline in the Colonic GHAS score at Week 12, Week 48, and Week 96 (among participants with Colonic histologic disease at baseline per GHAS)

- Statistical Analysis Plan Amendment 1 CNTO1959CRD3004
- Change from baseline in the Subject GHAS Score at Week 12, Week 48, and Week 96 (among participants with histologic disease at baseline per GHAS)
- GHAS-determined Histologic response at Week 12, Week 48, and Week 96 (among participants with histologic disease at baseline per Subject GHAS score)
- GHAS-determined Histologic ileal remission at Week 12, Week 48, and Week 96 (among participants with Ileal histologic disease at baseline per Ileal GHAS score)
- GHAS-determined Histologic colonic remission at Week 12, Week 48, and Week 96 (among participants with colonic histologic disease at baseline per Colonic GHAS score)
- GHAS-determined Histologic remission at Week 12, Week 48, and Week 96 (among participants with histologic disease at baseline per Subject GHAS score)
- GHAS-determined Histo-endoscopic response at Week 12, Week 48, and Week 96
- GHAS-determined Histo-endoscopic remission at Week 12, Week 48, and Week 96
- GHAS-determined Histo-endoscopic remission (Alternative definition) at Week 12, Week 48, and Week 96

Histologic endpoints - Geboes

- Geboes-determined Histologic response at Week 12, Week 48, and Week 96 (among participants with histologic disease at baseline per Subject Geboes score)
- Geboes-determined Histologic ileal remission at Week 12, Week 48, and Week 96 (among participants with Ileal histologic disease at baseline per Ileal Geboes score)
- Geboes-determined Histologic colonic remission at Week 12, Week 48, and Week 96 (among participants with colonic histologic disease at baseline per Colonic Geboes score)
- Geboes-determined Histologic remission at Week 12, Week 48, and Week 96 (among participants with histologic disease at baseline per Subject Geboes score)
- Geboes-determined Histo-endoscopic response at Week 12, Week 48, and Week 96
- Geboes-determined Histo-endoscopic remission at Week 12, Week 48, and Week 96
- Geboes-determined Histo-endoscopic remission (Alternative definition) at Week 12, Week 48, and Week 96

Histologic endpoints – RHI

- Change from baseline in the Ileal RHI score at Week 12, Week 48, and Week 96 (among participants with Ileal histologic disease at baseline per RHI)
- Change from baseline in the Colonic RHI score at Week 12, Week 48, and Week 96 (among participants with Colonic histologic disease at baseline per RHI)
- Change from baseline in the Subject RHI Score at Week 12, Week 48, and Week 96 (among participants with histologic disease at baseline per RHI)

- Statistical Analysis Plan Amendment 1 CNTO1959CRD3004
- RHI-determined Histologic response at Week 12, Week 48, and Week 96 (among participants with histologic disease at baseline per Subject RHI score)
- RHI-determined Histologic ileal remission at Week 12, Week 48, and Week 96 (among participants with Ileal histologic disease at baseline per Ileal RHI score)
- RHI-determined Histologic colonic remission at Week 12, Week 48, and Week 96 (among participants with colonic histologic disease at baseline per Colonic RHI score)
- RHI-determined Histologic remission at Week 12, Week 48, and Week 96 (among participants with histologic disease at baseline per Subject RHI score)
- RHI-determined Histo-endoscopic response at Week 12, Week 48, and Week 96
- RHI-determined Histo-endoscopic remission at Week 12, Week 48, and Week 96
- RHI-determined Histo-endoscopic remission (Alternative definition) at Week 12, Week 48, and Week 96

5.5.3. Analysis Methods

Through Week 24

Exploratory endpoints through Week 24 (eg, clinical remission, clinical response) will be tested regardless of the significance of the co-primary and secondary endpoints; the testing of these exploratory endpoints through Week 24 will not be controlled for multiplicity. Nominal p-values will be presented.

Descriptive statistics (i.e., N, mean, median, SD, IQ range, minimum, and maximum) will be used to summarize continuous variables. Counts and percentages will be used to summarize categorical variables. Graphical data displays (e.g., line plots) may also be used to summarize the data.

The estimand approach and analysis methods specified in Sections 5.4.2.1 and Section 5.4.3.1 for the secondary endpoints will apply to binary endpoints. The ICEs are the same as those specified in Sections 5.4.2.1

For continuous endpoints, the attributes of the estimands will be the same as those specified for the secondary endpoints relative to **Study Intervention**, **Population**, and **ICEs**. If a participant has an ICE in categories 1-3, 5, or 6, baseline values will be assigned from the point of ICE onward. For participants experiencing ICE 4, the associated ICE event will be ignored and any data observed after the associated ICE event will be used for the analysis.

Continuous efficacy endpoints that are collected at multiple post baseline time points through a given visit will be compared using a Mixed Model Repeated Measures (MMRM). The model will include all available data from all treatment groups through that visit for assessing efficacy.

The MMRM model will be used to test the difference between the combined guselkumab group or each guselkumab group versus the placebo group. This model relies on the MAR assumption for the missing responses. Under the assumption of MAR, the missing data will be accounted for through correlation of repeated measures in the model.

The explanatory variables of the MMRM model will include treatment group, visit, applicable baseline score, BIO-Failure status (yes, no), baseline CDAI (\leq 300 or > 300), baseline SES-CD (\leq 12 or > 12), an interaction term of visit with treatment group, and an interaction term of visit with applicable baseline score. Change from baseline in CDAI endpoints will not include CDAI strata in the model, as the baseline CDAI is already included as a factor.

The estimates of the treatment difference between the combined guselkumab group or each guselkumab group versus the placebo group will be provided by the difference in the least squares means (LSmeans). The 95% confidence interval (CI) for the differences in LSmeans and p-values will be calculated based on the MMRM. An unstructured covariance matrix for repeated measure within a subject will be used. The F-test will use Kenward-Roger's approximation for degrees of freedom. In case of lack of convergence, empirical structured covariances will be used in the following order until convergence is reached: 1) Toeplitz 2) first order Autoregressive Moving Average. If the normality assumption is in question, an appropriate transformation will be used.

Continuous endpoints involving SES-CD or histologic endpoints that are measured only at Week 12 will be compared using an analysis of covariance (ANCOVA) with treatment as a fixed factor, and baseline score, CDAI (\leq 300 or > 300), baseline SES-CD (\leq 12 or > 12), and Bio-Failure status (yes or no) as covariates. Continuous endpoints involving SES-CD will not include SES-CD strata in the model. Multiple imputation (MI) will be used for imputing missing Total SES-CD data under the assumption that the data are missing at random (MAR). For continuous endpoints involving GHAS and RHI, no imputation will be performed for missing GHAS or RHI values; the missing values will remain as missing. For binary endpoints, NRI will be used to impute missing GHAS, Geboes and RHI endpoints.

After Week 24

Two exploratory endpoints (clinical remission at Week 48, endoscopic response at Week 48) will be controlled for multiplicity. The analyses of the two endpoints will be placed after the 6 sequential tests of the co-primary and secondary endpoints in the multiple testing procedure described in Section 5.4.3.1. If all 6 p-values are <0.05, the testing procedure will continue with the 4 tests of these two endpoints (clinical remission at Week 48, endoscopic response at Week 48, for both dose groups) using the Hochberg procedure (Y Hochberg, Biometrika (1988), 75, 4, pp.800-2) with a 2-sided alpha of 0.05. The Type I error will be controlled over the co-primary, secondary, and these two Week 48 exploratory endpoints in this multiplicity-controlled testing procedure.

The testing of other exploratory endpoints will not be controlled for multiplicity, and nominal p-values will be provided.

Similar methodology used for analyzing endpoints through Week 24 will be applied to the endpoints analyses after Week 24. Specifically, the estimand approach and analysis methods specified in Sections 5.4.2.1 and Section 5.4.3.1 for the secondary endpoints will apply to the two exploratory binary endpoints (clinical remission at Week 48, endoscopic response at Week 48). Unless otherwise specified, the ICEs are the same as those specified in Sections 5.4.2.1.

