6.8.1.1. Oral Corticosteroids Tapering

At Week 12, all participants who were taking corticosteroids at Week 0 must begin tapering corticosteroids. This tapering is mandatory, unless not medically feasible, and should follow the recommended schedule shown in Table 6. If participants experience worsening of their disease activity while tapering corticosteroids, further dose decreases may be suspended, and/or their oral corticosteroid dose may be temporarily increased if deemed necessary by the investigator. The oral corticosteroid dose, however, may not be increased above the Week 0 dose unless due to medical

necessity. For participants whose corticosteroid taper is interrupted, investigators are encouraged to resume tapering within 4 weeks. Tapering may exceed this schedule only if warranted by medical necessity (eg, participant experiencing corticosteroid-related side effects).

Table 6: Recommended Tapering Schedule for Oral Corticosteroids

Recommended Tapering Schedule for Oral Corticosteroids (Other Than Budesonide)				
Dose >15 mg/day prednisone or equivalent	Taper daily dose by 5 mg/week until receiving			
	10 mg/day, then continue tapering at 2.5 mg/week until			
	0 mg/day			
Dose 11 to 15 mg/day prednisone or	Taper daily dose to 10 mg/day for 1 week, then continue			
equivalent	at 2.5 mg/week until 0 mg/day			
Dose ≤10 mg/day prednisone or equivalent	Taper daily dose by 2.5 mg/week until 0 mg/day			
Recommended Tapering Schedule for Oral Budesonide				
Participants receiving budesonide should have their daily dose tapered by 3 mg every 3 weeks until				
0 mg/day.				

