5.4.2. Estimands

5.4.2.1. Estimands for the Secondary Endpoints

Secondary Estimand of Clinical Remission at Week 24 (Main Estimand 5)

The following describes the attributes of the Main Estimand 5.

Treatment by Week 24:

Experimental:

- Guselkumab ^{CCI} q4w (Weeks 0, 4, and 8) followed by guselkumab ^{CCI} q4w (Weeks 12, 16, and 20)
- Guselkumab ^{CCI} q4w (Weeks 0, 4, and 8) followed by guselkumab ^{CCI} q8w starting at Week 16

Control: Placebo SC q4w (Weeks 0, 4, 8, 12, 16, and 20)

Population: Participants with moderately to severely active Crohn's disease

Variable (Endpoint):

A binary response variable (response/nonresponse) where response is defined as achieving CDAI score <150 at Week 24 without experiencing any of the ICEs in categories 1, 2, 3, 5 and 6 as outlined below prior to the Week 24 visit.

Intercurrent events and corresponding strategies:

ICE Identifier	ICE Description	Corresponding Strategy
1	A Crohn's disease-related surgery (with the exception of minor procedures such as drainage of a superficial abscess or seton placement, etc.)	Composite
2	A prohibited change in Crohn's disease medication (See Appendix 2)	Composite
3	Discontinuation of study intervention due to lack of efficacy or an AE of worsening of Crohn's Disease	Composite
4	Discontinuation of study intervention due to COVID-19 related reasons (excluding COVID-19 infection) or regional crisis	Treatment Policy
5	Discontinuation of study intervention due to COVID-19 infection or for reasons other than those specified in ICE categories 3 and 4	Composite
6	Meets rescue criteria as determined by the IWRS	Composite

The composite strategy assesses the treatment effects not only based on the variable measurements, but also based on ICEs. This estimand acknowledges that having an ICE in categories 1-3, 5 and 6 is an unfavorable outcome. For participants experiencing ICE category 4, the treatment policy strategy considers the occurrence of ICE category 4 is irrelevant in defining the treatment effect.

Population-level summary:

Difference in proportions of responders (according to the **Variable** defined above) between each guselkumab group and the placebo group.

Secondary Estimand of PRO-2 Remission at Week 12 (Main Estimand 6)

The same estimand (except for the "Variable" attribute) that is specified for the co-primary endpoint analyses will be used.

Variable (Endpoint):

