5.5.2.2. Corticosteroid related endpoints

- Corticosteroid-free clinical remission at Week 24
- Corticosteroid-free clinical remission at Week 48
- 90-day corticosteroid-free clinical remission at Week 48
- Average daily prednisone-equivalent (P.Eq) corticosteroid dose (excluding budesonide and beclomethasone dipropionate) over time in participants who were receiving corticosteroids other than budesonide and beclomethasone dipropionate at baseline
- Change from baseline in the average daily prednisone equivalent (P.Eq) oral corticosteroids dose (mg/day; excluding budesonide and beclomethasone dipropionate) at each visit over time in participants who were receiving oral corticosteroids other than budesonide and beclomethasone dipropionate at baseline
- Number of participants who were not receiving concomitant corticosteroids at Weeks 24, 48, 96 in participants who were receiving concomitant corticosteroids at baseline
- Number of participants who were not receiving corticosteroids for at least 90 days prior to Weeks 48, 96 in participants who were receiving concomitant corticosteroids at baseline

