6.2. Appendix 2 Prohibited Changes in CD Medications (Intercurrent Event 2)

(1) **Prohibited medications**

Initiation of the following prohibited medications after Week 0

- a. Immunomodulatory agents other than AZA, 6-MP, or MTX (including, but not limited to, 6-thioguanine, cyclosporine, mycophenolate mofetil, tacrolimus, and sirolimus).
- Immunomodulatory biologic agents (including, but not limited to, TNFα antagonists, natalizumab, ustekinumab, rituximab, vedolizumab).
- c. Experimental Crohn's disease medications (including, but not limited to, upadacitinib, filgotinib, ozanimod, etrolizumab, brazikumab, mirikizumab, risankizumab, and andecaliximab).
- d. Thalidomide or related agents.

(2) Corticosteroids

The occurrence of the following changes in corticosteroid usage during induction treatment (ie, before week 12), OR, between week 36 and week 48, including changes initiated before week 36 and continued after week 36, unless otherwise specified.

- a. Initiation of oral corticosteroids (including budesonide and beclomethasone dipropionate), parenteral, or rectal corticosteroids due to worsening Crohn's disease.
- b. Increase in the dose of oral corticosteroids (including budesonide and beclomethasone dipropionate), as specified below, above the baseline dose due to worsening Crohn's disease.
 - i. Oral corticosteroids > 5 mg/day (prednisone equivalent)
 - ii. Oral budesonide > 3 mg/day
 - iii. Oral beclomethasone dipropionate > 5 mg/day
- c. Initiation of oral corticosteroids (including budesonide and beclomethasone dipropionate) due to reasons other than worsening Crohn's disease for more than 7 days during induction treatment, OR, for more than 28 days during maintenance treatment.
- d. Increase in the dose of oral corticosteroids (including budesonide and beclomethasone dipropionate), as specified below, above the baseline dose due to reasons other than worsening Crohn's disease for more than 7 days during induction treatment, OR, for more than 28 days during maintenance treatment.
 - i. Oral corticosteroids > 5 mg/day (prednisone equivalent)
 - ii. Oral budesonide > 3 mg/day
 - iii. Oral beclomethasone dipropionate > 5 mg/day

(3) Immunomodulator agents

- a. Initiation of oral 6-MP/AZA due to worsening Crohn's disease.
- b. Initiation of oral, subcutaneous, or intramuscular MTX due to worsening Crohn's disease.
- c. Increase in the dose of oral 6-MP/AZA above the baseline dose due to worsening Crohn's disease.

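### For the two steroid-dose endpoints, assigning the baseline value after an intercurrent event turns a steroid increase that is itself the event into zero change

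*SAP*

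**What the plan says.** SAP 5.5.3 sets one rule for continuous endpoints: "If a participant has an ICE in categories 1-3, 5, or 6, baseline values will be assigned from the point of ICE onward". The rule stands under the heading for analyses through Week 24. For later visits the same section says only that similar methodology applies.

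SAP 5.5.2.2 lists two continuous dose endpoints: "Average daily prednisone-equivalent (P.Eq) corticosteroid dose (excluding budesonide and beclomethasone dipropionate) over time" and "Change from baseline in the average daily prednisone equivalent (P.Eq) oral corticosteroids dose". Both are restricted to participants taking steroids other than budesonide and beclomethasone at baseline. Neither 5.5.2.2 nor 5.5.3 exempts them from the rule.

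SAP Appendix 2 (6.2) defines ICE 2. Its corticosteroid item includes "Increase in the dose of oral corticosteroids (including budesonide and beclomethasone dipropionate), as specified below, above the baseline dose due to worsening Crohn's disease", with a threshold of more than 5 mg/day in prednisone equivalents. The item applies to changes "during induction treatment (ie, before week 12), OR, between week 36 and week 48", and the second window also takes in changes begun before Week 36 and continued beyond it.

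SAP 5.4.2.1 handles ICE categories 1-3, 5 and 6 by the composite strategy and describes them as unfavorable outcomes. ICE 6 is "Meets rescue criteria as determined by the IWRS", and it applies in every arm. On tapering, Protocol 6.8.1.1 states: "At Week 12, all participants who were taking corticosteroids at Week 0 must begin tapering corticosteroids". The only stated exception is where tapering is not medically feasible.

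**The concern.** For a disease score, the baseline value is a sensible stand-in for no benefit. For a drug dose it is not always the unfavorable value. When the intercurrent event is a dose increase, the participant's recorded dose is above baseline, and the rule replaces it with something lower. The endpoint exists to measure steroid use, and the rule removes the clearest sign that steroid use went up.

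At stake is whether the two dose summaries can be read as evidence of steroid sparing. Arms with more ICE 2 increases have more of them erased, so both the arm means and the contrast between arms can move.

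**Working it through.** The plan states no figure on this point, so there is none to reproduce. The check applies the rule literally to example doses.

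**Inputs**
- Rule after ICE 1-3, 5 or 6: assigned dose = baseline dose B (SAP 5.5.3).
- ICE 2 increase: recorded dose R exceeds B by more than 5 mg/day, for worsening disease (SAP Appendix 2).
- Taper above 15 mg/day: 5 mg per week down to 10 mg/day, then 2.5 mg per week to zero, starting at Week 12 (Protocol Table 6).
- Maximum prednisone-equivalent dose at entry: 40 mg/day (Protocol 5.1, criterion 7b).
- Steroid-use, ICE 2 and rescue rates: not given. The values below are assumptions.

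**Step 1: one participant with an ICE 2 increase.** Recorded change = R - B. Analysed change = B - B = 0. Understatement = R - B.

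| Baseline (mg/day) | Raised to | Recorded change | Analysed change |
|---|---|---|---|
| 20 | 30 | +10 | 0 |
| 20 | 40 | +20 | 0 |
| 10 | 40 | +30 | 0 |

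**Step 2: when the overwrite applies.**

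| Timing of the increase for worsening disease | ICE 2? | Dose analysed |
|---|---|---|
| Before Week 12 | Yes | Baseline |
| Begun in Weeks 12-36, ended before Week 36 | No | Recorded, unless another ICE applies |
| Begun before Week 36, continued past it | Yes | Baseline |
| Begun in Weeks 36-48 | Yes | Baseline |

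The first row falls directly under the rule as written. The last two depend on the similar-methodology sentence for visits after Week 24.

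**Step 3: arm mean.** If a share f of an arm's baseline users has a mean ICE 2 increase of D, the simple arm mean is understated by f x D. With D = 20 mg/day (assumed):
- f = 5%: 0.05 x 20 = 1 mg/day
- f = 10%: 0.10 x 20 = 2 mg/day
- f = 20%: 0.20 x 20 = 4 mg/day

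The contrast moves by the difference between arms. With 20% in one arm and 5% in the other, that is 4 - 1 = 3 mg/day, in favor of the arm with more increases. With equal shares and equal mean increases it is zero. These are shifts in raw means, not in the model estimate.

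**Step 4: ICE 6, for comparison.** From 40 mg/day, Table 6 takes six 5-mg steps to 10 mg and four 2.5-mg steps to zero. That is ten weekly steps, ending at about Week 21-22 if uninterrupted. At Week 24 such a participant's recorded change is -40 mg/day. If he or she met rescue criteria, the analysed change is 0.

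Now assume a common 20 mg/day baseline and everyone truly at zero by Week 24. Rescue-criteria rates of 30% (placebo) and 15% (guselkumab) give analysed mean changes of -20 x 0.70 = -14 and -20 x 0.85 = -17, a difference of 3 mg/day. Rates of 50% and 20% give -10 and -16, a difference of 6. Equal rates give none. Here the assigned value is less favorable than the recorded one, which is the direction a composite strategy intends. In Step 1 the direction is reversed.

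**Step 5: the repair.** Assign max(B, R). For 10 raised to 40: max(10, 40) = 40, change +30, so the increase is kept. For a taper from 20 to 0 after sham rescue: max(20, 0) = 20, change 0, as the SAP has it now.

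**The case against.** The strongest reply is that assigning baseline is the declared composite strategy carried over to continuous endpoints: a participant who has failed gets no credit from that point on. A composite value does not claim to be the dose taken. For ICE 6 this stands.

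A reader might infer that recording a sham-rescued guselkumab participant at full baseline dose, after a mandatory taper, is equally an error. The documents do not support that. SAP 5.4.2.1 makes meeting rescue criteria an unfavorable outcome in every arm, and withholding steroid-sparing credit follows from it. Using recorded doses instead would credit placebo with tapers achieved on rescue guselkumab. Nor can completed tapers be assumed: Protocol 6.8.1.1 allows a taper to be suspended, or the dose temporarily raised, when disease worsens. SAP 5.7.2 and 5.7.4 do set ICE 6 aside, but for exploratory immunogenicity and exposure analyses with a different purpose.

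A reader might also infer that the steroid results as a whole fail to describe steroid use. That goes too far. For corticosteroid-free remission at Weeks 24 and 48, and its 90-day form at Week 48, an ICE 2 increase counts as non-response. Only the two dose summaries are affected.

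The defense does not reach ICE 2 increases. Assigning a dose below the recorded one does more than withhold credit: it improves the participant's value because of the failure event.

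**Conclusion.** The point holds for steroid increases. As written, SAP 5.5.3 analyses an ICE 2 increase in prednisone-equivalent dose as zero change, which contradicts the SAP's own description of that event as unfavorable. This is certain from the text for increases before Week 12. For Weeks 36-48 it rests on reading the similar-methodology sentence as carrying the rule forward.

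The size cannot be fixed from the documents. The 1 to 4 mg/day range assumes 5% to 20% of baseline users with a mean increase of 20 mg/day. The direction of any bias in the contrast depends on which arm has more such increases. If that is placebo, the rule hides part of a guselkumab advantage.

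Both endpoints are exploratory with nominal p-values. The co-primary, secondary and multiplicity-controlled Week 48 endpoints are untouched.

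**What to change.** Add to SAP 5.5.3: *For the corticosteroid dose endpoints in 5.5.2.2, after an ICE in categories 1-3, 5 or 6 the larger of the baseline dose and the recorded dose is assigned at each visit.* State that the same rule applies after Week 24.

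The wording covers every composite category on purpose. If only ICE 2 were exempted, a participant whose steroids were raised and who then stopped treatment for lack of efficacy (ICE 3) would still be reset to baseline. The composite strategy is kept, and no increase is erased.

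As a supplementary descriptive display, summarise recorded doses by visit regardless of ICE, with rescued placebo participants' post-rescue doses shown separately, as the safety tables in SAP 5.6 already do. Tapers completed after rescue or sham rescue then become visible without changing the main comparison.

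The cost is one SAP sentence and one extra table. Protocol 6.8 already requires dose and treatment period to be recorded for all concomitant therapy, so no new data are needed.
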